5.2 Exclusion Criteria

Participants are excluded from the study if any of the following criteria apply:

Medical Conditions

1. Any condition, including any uncontrolled disease state that in the Investigator's opinion constitutes an inappropriate risk or a contraindication for participation in the study or that could interfere with the study objectives, conduct, or evaluation.
2. An active second malignancy or evidence of disease of cancer (other than MM) before the date of enrollment (exceptions are squamous and basal cell carcinomas of the skin and carcinoma in situ of the cervix, or malignancy that in the opinion of the Investigator, with concurrence with the Sponsor's Medical Monitor, is considered cured with minimal risk of recurrence within 3 years).
3. Cerebrovascular accident/stroke (< 6 months prior enrollment) or neurologic instability per clinical evaluation due to tumor involvement of the CNS.
4. Diagnosis of fever within 1 week prior to study intervention administration.
5. Uncontrolled concurrent illness (e.g., serious uncontrolled diabetes [blood glucose > 250 mg/dL], or psychiatric illness/social situations that would limit compliance with the study requirements).
6. Active symptomatic fungal, bacterial and/or viral infection. Individuals with known or seropositive testing for human immunodeficiency virus (HIV) or actively infected viral hepatitis (B or C) are excluded. However, individual with Hepatitis C treated with curative therapy are not considered actively infected.
7. Plasma cell leukemia ($> 2.0 \times 10^9/L$ circulating plasma cells by standard differential), active CNS MM or POEMS syndrome (polyneuropathy, organomegaly, endocrinopathy, monoclonal protein, and skin changes) or amyloidosis.
8. Impaired cardiac function
 - Left ventricular ejection fraction < 45% defined by echocardiography (at Screening)
 - Serious arrhythmia
 - Unstable angina pectoris
 - New York Heart Association heart failure Class III and IV
 - Myocardial infarction within the last 12 months prior to study entry
 - Symptomatic pericardial effusion
9. Peripheral neuropathy of Grade ≥ 2 with pain
10. Active graft versus host disease
11. Life expectancy of < 4 months.

12. Current significant cardiac conduction abnormalities, including corrected QT interval (QTc) prolongation of > 450 ms for males and > 470 ms for females must be confirmed on Day 1 Cycle 1.

Prior/Concomitant Therapy

13. Participant who received chemotherapy, extensive radiation therapy (involving $\geq 30\%$ of bone marrow), vertebroplasty, kyphoplasty or biological therapy (e.g., antibodies, erythropoietin) within 2 weeks (6 weeks for nitrosourea, mitomycin-C) or 5 half-lives prior to dosing or who have been treated with small molecule therapeutics or investigational agents within 4 weeks prior to starting study intervention with M3258 or who have not recovered from the side effects of such therapy to Baseline or Grade 1 (except for alopecia or potentially neuropathy).
14. Hormonal therapies acting on the hypothalamic-pituitary-gonadal axis (i.e., luteinizing hormone-releasing hormone agonist/antagonists).
15. Steroid therapy for antineoplastic intent taken < 7 days prior to the first dose of study intervention. Includes participants who have received a cumulative dose of corticosteroid greater than or equal to the equivalence of 140 mg prednisone or a single dose of corticosteroid greater than or equal to the equivalence of 20 mg/day dexamethasone within the 2-week period before first dose of study intervention.
16. Participant currently receiving (or unable to stop using prior to receiving the first dose of study intervention) medications known to be strong inhibitors or inducers of CYP3A or any herbal supplements known to inhibit or induce CYP3A. Comedication and herbal supplements must stop at least 7 days before the first administration of the study intervention (for details see Section 6.5.3).
17. Participant currently receiving (or unable to stop using prior to receiving the first dose of study intervention) medications or herbal supplements known to be inhibitors of P-gp. Comedication must stop at least 7 days before the first administration of the study intervention (for details see Section 6.5.3).
18. Participant currently receiving (or unable to stop using prior to receiving the first dose of study intervention) medications known to prolong the QT/QTc interval. Comedication must stop at least 7 days before the first administration of the study intervention (a list of medication is attached in the [Appendix 4: Prohibited Comedication Prolonging the QT/QTc Interval](#)).
19. Participant has received autologous stem cell transplant within 12 weeks before the first dose of study intervention, or the participant has previously received an allogenic stem cell transplant (regardless of timing).

Diagnostic Assessments

Not applicable

Other Exclusions

Part B only:

20. Participants planning to undergo a stem cell transplant should not be enrolled to reduce disease burden prior to transplant.

5.3 Lifestyle Considerations

5.3.1 Meals and Dietary Restrictions

Participants will be instructed to refrain from consumption of grapefruit, grapefruit juice, Seville oranges, Seville orange marmalade, or other products containing grapefruit or Seville oranges, St. John's wort as well as any other CYP3A inhibiting/inducing or P-gp inhibiting herbal supplements starting at least 7 days before the first administration of the study intervention and during the study intervention administration.

Part A and Part B

Participants will receive study intervention daily with restriction of food for 1 hour before and 2 hours after dose administration except for the food effect evaluation on Part B Day 1 Cycle 2.

Part B Day 1 Cycle 2 – Food Effect Evaluation

Day 1 Cycle 2 will be an evaluation of a possible effect of food on the PK. All participants will be allocated to 1 of 2 treatment schedule cohorts (as long as safety of the participant is not endangered [i.e., diabetic participant]). The first 9 participants in Part B will be allocated to Schedule A (study treatment without food) and subsequent 9 participants will receive Schedule B (study treatment with food), unless there has been a change in dose. At the interim analysis, the need for additional participants for food effect will be determined without affecting the overall number of participants in the study. Then allocation will be alternating ABAB, etc. Upon enrollment, the site will receive the food-schedule assignment for the participant from the medical monitor or a designee.

- **Schedule A:** all participants of this cohort will receive the regular dose and regimen of M3258 without food. They will fast for 10 hours (i.e., no food [except as noted below] from midnight onwards) before administration of study intervention until at least 4 hours after dosing.
- **Schedule B:** all participants of this cohort will receive the regular dose and regimen of M3258 with food. They will receive a regular breakfast; 30 minutes after start of the breakfast all participants will receive a regular dose of M3258. The regular breakfast contains approximately 400-500 kcal with fat contributing to approximately 150 kcal. M3258 will be taken with 200 mL of water. After administration of study intervention, the participants will fast for at least 4 hours.

During the PK sampling, participants will be allowed to drink water as they desire except 1 hour before and after administration of study intervention.

M3258 will be taken with 200 mL of water.

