- c: Actual collection times should be collected in the electronic Case Report Form along with the times of the last dose administration.
- d: Triple ECG for the QT/QTc analysis after at least 10 minutes' rest and within 2 minutes and have to be taken before any blood sampling. See [Table 1](#) and [Table 2](#) for 12-lead Safety ECG timing (note that triple ECG for the QT/QTc analysis here is listed as 12-lead QTc Assessment in Tables 1 and 2).

Table 6 Schedule of Electrocardiogram, Pharmacokinetic, and Biomarker Assessments during Dose Expansion - Part B (for 21- and 28-day cycles)

Treatment Day ^a	Time h (± min) ^{b,c}	ECG ^d	PK M3258	PK dexamethasone	LMP7 activity & β5c	CCI
D1 C1	Predose		X		X	
	1 (± 5)		X			
	2 (± 10)		X		X	
	3 (± 15)		X			
	4 (± 15)		X			
	5 (± 15)		X			
	6 (± 15)		X		X	
D2 C1 ^f	24 (Predose)		X		X	
D8 C1	Predose	X	X		X	
	1 (± 5)		X			
	2 (± 10)	X	X		X	
	3 (± 15)		X			
	4 (± 15)	X	X			
	5 (± 15)		X			
	6 (± 15)	X	X		X	
D1 C2	Predose		X ^e	X ^e		
	1 (± 5)		X ^e	X ^e		
	2 (± 10)		X ^e	X ^e		
	3 (± 15)		X ^e	X ^e		
	4 (± 15)		X ^e	X ^e		
	5 (± 15)		X ^e			
	6 (± 15)		X ^e		X ^e	
	8 (± 30)		X ^e			

β5c = Constitutive proteasome subunit β5; C = Cycle; D = Day; ECG = Electrocardiogram; LMP7 = Large multifunctional protease 7; CCI [REDACTED]; Pd = Pharmacodynamics; PK = Pharmacokinetics.

a: Table 6 is applicable for all proposed regimens in Part B.

b: At visits where assessment time points (ECG, PK and PD) coincide with each other

- 1) Perform vital signs assessments at first
- 2) ECG assessments slightly before the specific collection time point
- 3) PK assessments at scheduled collection time point and
- 4) Pd assessments as last assessment

c: Actual collection times should be collected in the eCRF along with the times of the last dose administration.

- d: Triple ECG for the QT/QTc analysis after at least 10-minutes rest and within 2 minutes and have to be taken before any blood sampling. See [Table 3](#) and [Table 4](#) for 12-lead Safety ECG timing (note that triple ECG for the QT/QTc analysis here is listed as 12-lead QTc Assessment in Tables 3 and 4).
- e: PK samples for food effect evaluation taken for at least the first 18 participants. Decision on sampling in further participants will be taken during interim analysis.
- f: For participants in the safety run-in and the first 3 participants at a new dose.

2**Introduction**

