
 • To investigate the PK profile of M3258 (single and multiple dose exposure) when co-administered with dexamethasone in participants with RRMM 	
 • PK profile of M3258 in terms of C_{max}, AUC_{0-t}, AUC_{0-24} at Day 1 Cycle 1, (single dose): predose, 1, 2, 3, 4, 5, and 6 and 24h after administration • PK profile of M3258 in terms of C_{max}, AUC_{0-24} at Day 8 Cycle 1, (multiple dose): predose, 2, 4, and 6h after administration
Exploratory 
 • To investigate the changes in the pharmacodynamic marker of M3258 when co-administered with dexamethasone in participants with RRMM • To investigate further PK parameters of M3258 (single and multiple dose exposure) when co-administered with dexamethasone in participants with RRMM • To investigate the food effect on the PK of M3258 when co-administered with dexamethasone in participants with RRMM 	
 • Changes in LMP7 activity on Day 1 Cycle 1 pre and postdose and Day 8 Cycle 1 pre and postdose • PK profile of M3258 in terms of t_{max}, t_{lag}, $t_{1/2}$, CL/F, V_z/F at Day 1 Cycle 1, (single dose): predose, 1, 2, 3, 4, 5, 6 and 24h after administration • PK profile of M3258 in terms of $AUC_{0-\infty}$, t_{max}, t_{lag}, $t_{1/2}$, CL_{ss}/F, at Day 8 Cycle 1, (multiple dose): predose, 2, 4, and 6 h after administration • PK profile of M3258 in terms of dose-normalized C_{max}, AUC_{0-t}, AUC_{0-24} for single and multiple dose • Area under the plasma concentration-time curve (AUC_{0-8h}) with and without food from time zero (= dosing time) to 8 h and C_{max} of M3258 observed on Day 1 Cycle 2: predose, 1, 2, 3, 4, 5, 6 and 8 h postdose

Objectives	Endpoints

 To investigate the relationship between exposure with M3258 and QTc, when co-administered with dexamethasone in participants with RRMM 	
 Relative changes from Baseline in ECG parameters (QTc) in relation to M3258 plasma concentration: all times after single and multiple dosing with concurrent QTc and plasma concentration assessments

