The SMC will recommend a dose and regimen for the expansion cohort based on an integrated review on all available safety, tolerability, PK, Pd (including LMP7 activity) and initial efficacy data.

Residual LMP7 activity reaching a plateau comparing at least 3 increasing dose levels will support the RDE selection.

At least 6 participants need to be treated at the selected RDE as M3258 monotherapy. Additionally, the median estimated DLT rate of the RDE needs to be $\leq 25\%$ and the 75% percentile of the estimated DLT probability of the RDE needs to be below 30%.

If further data is required to determine the RDE, additional participants may be enrolled in Part A (see Section 9.2).

Dose Expansion Part B

Once an RDE (dose and regimen) of M3258 has been defined which is considered safe by the SMC, dose expansion (Part B) may begin. Initiation of Part B may start without reaching the MTD in Part A; dose escalation for defining the monotherapy MTD (Part A) may proceed in parallel.

Participants with MM whose disease has progressed following > 3 lines of therapy for whom no effective standard therapy exists (see definition in Section 5) will be enrolled. In Part B, participants will receive M3258 at the RDE selected in Part A in combination with dexamethasone at a cumulative dose of 40 mg / week. The first 2 cohorts of 3 participants each (first 6 participants) will be used for a safety run-in. The participants in these 2 cohorts will be enrolled in a staggered approach. Each cohort of the safety run-in will be evaluated by the SMC for the prespecified DLT criteria (see Section 6.6) of this combination before additional participants are enrolled. The SMC meetings will be held after the first 3 and 6 participants have finished Cycle 1 or discontinued treatment. The SMC will evaluate safety, cumulative

and unacceptable toxicity (see definition of acceptable toxicity below). SMC decisions on potential dose adjustments in the safety run-in (and later on) will be supported by Bayesian modeling. After the safety run-in, SMC meetings will be held at the completion of Cycle 1 or discontinuation of treatment for every 6 participants (without pausing enrollment) in order to assess safety, cumulative and unacceptable toxicity of all participants in the expansion cohort, unless a change in dosing has occurred. In case dosing in the expansion cohort was changed, the next SMC will be held after 3 participants have finished the DLT period or discontinued.

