Participants who did not experience a DLT and who either did not receive at least 80% of the planned cumulative dose of treatment during the DLT period, or at least 80% of the planned

administrations, or did not complete the DLT observation period will not be considered for DLT evaluation and in the Bayesian model. An SMC meeting with selection of dose for next cohort will also be held if not all participants in a cohort are evaluable (e.g., if a participant missed more than 20% of treatment in the first cycle for any reason other than a DLT).

The SMC might modify the schedule of PK and Pd sampling based on emergent data. However, the total blood volume taken for PK and Pd samples will not exceed blood volume described in this protocol or the Laboratory Manual.

For the expansion part of the study, the SMC will monitor the safety of M3258 at the recommended dose with dexamethasone and may recommend by consensus on continuation at the same dose, change in dose (only to doses declared safe by SMC in monotherapy), modifications of the study protocol, or stop of expansion cohort. The same DLT criteria as for the monotherapy dose escalation will apply. Additional safety stopping rules apply as outlined in Section 7.1.

The SMC will evaluate the safety of the combination therapy after 3, 6, (safety run-in) and subsequently every 6 participants finished their DLT period or discontinued, unless a change in dosing has occurred. In case the dosing in the expansion cohort was changed, the next SMC will be held after the next 3 participants have finished the DLT period or discontinued and then the SMCs are scheduled every 6 participants having finished the DLT period or discontinued.

For SMCs in the safety run-in and the first SMC after a dose change, dosing of new participants can only start after SMC has decided to proceed (including on what dose). For all other SMCs there is no pause in enrollment.

The SMC decisions in expansion cohort will also be supported by a two-parameter Bayesian logistic regression model. For details on the model, see Section 9.4.2.

The SMC may modify the frequency of meetings as deemed appropriate during the study.

After the evaluation of the food effect in 15 participants in Part B, the SMC will take the decision whether to increase the number of participants which are to be included in the food effect evaluation.

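### The Part B food effect compares a fasted first block of 9 with a fed second block of 9, so food cannot be separated from enrolment order or the safety run-in, and no allocation is given after a dose change

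*Protocol*

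**What the plan says.** Protocol 5.3.1 makes Day 1 Cycle 2 of Part B the food-effect day. Each participant has one food condition: Schedule A (a 10-hour fast before the dose and at least 4 hours after it) or Schedule B (a regular breakfast starting 30 minutes before the dose). The rule is "The first 9 participants in Part B will be allocated to Schedule A (study treatment without food) and subsequent 9 participants" go to the fed schedule; a proviso in the same sentence lifts this rule once the dose has been changed. If the interim analysis asks for more food-effect participants, "Then allocation will be alternating ABAB, etc". Section 6.3.1 on intervention assignment is marked not applicable. The medical monitor or a designee sends each site its food assignment at enrolment.

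Section 4.1 adds: "The first 2 cohorts of 3 participants each (first 6 participants) will be used for a safety run-in". Footnote e of Table 6 adds: "PK samples for food effect evaluation taken for at least the first 18 participants".

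The endpoint in Table 8 is exploratory: AUC0-8h and Cmax of M3258 on Day 1 Cycle 2, "with and without food from time zero (= dosing time) to 8 h". Section 9.4.4 has a preliminary evaluation at the interim analysis to indicate whether to continue or stop the food evaluation. Section 10 says: "After the evaluation of the food effect in 15 participants in Part B, the SMC will take the decision" on whether to include more. No precision, target effect or analysis method is stated. SAP section 5 leaves the food effect to a later version.

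**The concern.** Within the first 18 participants, food condition and enrolment block are the same variable. Anything that changes as Part B enrols (site mix, patient mix, handling of sampling days, run-in practice) appears as a food effect or hides one. No analysis comparing the two groups can undo this, because neither group contains anyone from the other's enrolment period. This contrast informs the decision to extend or stop the food evaluation.

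The dose-change clause leaves a second gap. Section 4.1 ties upward dose steps to data from the run-in, which lies inside the fasted block. The 9+9 rule then stops applying, with no statement of how later participants are allocated or which of them form the contrast. The count of at least the first 18 in Table 6 carries on unchanged.

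**Working it through.** **The plan's own count.** 9 fasted + 9 fed = 18, which agrees with footnote e of Table 6. There is no power or precision figure to reproduce.

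**Balance under the stated rule and under alternation (ABAB) from participant 1**

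| | 5.3.1 | ABAB |
|---|---|---|
| Run-in participants, fasted / fed | 6 / 0 | 3 / 3 |
| Mean enrolment position, fasted v fed | 5 v 14 | 9 v 10 |
| Split among the first 15 enrolled | 9 v 6 | 8 v 7 |

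A random 9:9 allocation would put all six run-in participants in the fasted group with probability C(12,3)/C(18,9) = 220/48,620 = 0.0045.

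**Size of a spurious food effect (the drifts and shifts are assumptions).**
- Log-linear drift d per enrolled participant: the false fed/fasted ratio is exp(9d) under 5.3.1 and exp(d) under ABAB. For d = 1%, 2% and 3% this gives 1.09, 1.20 and 1.31, against 1.01, 1.02 and 1.03.
- Run-in exposure r times that of later participants: the false ratio is r^(-6/9), because 6 of the 9 fasted are run-in. For r = 1.1, 1.2 and 1.3 this gives 0.94, 0.89 and 0.84; under ABAB it is 1.00.

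**After a dose change.** One reading is that the count restarts. If the dose changed after participant 6, the first 18 would be 6 fasted at the old dose, then 9 fasted and 3 fed at the new dose. The protocol neither adopts nor excludes this reading.

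**What the Cycle 1 samples can add.** Table 6 samples M3258 at predose and 1, 2, 3, 4, 5 and 6 h on Day 1 and Day 8 of Cycle 1, and at the same times plus 8 h on Day 1 Cycle 2. Cycle 1 therefore supports Cmax and AUC0-6, but not AUC0-8h. Table 8 lists Day 8 as predose, 2, 4 and 6 h only, which conflicts with Table 6.

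Precision on the log scale, as a 90% CI around a true ratio of 1 with 9 v 9 participants. Let T be the total CV of one exposure measurement and w the within-participant CV. Both are assumptions; the documents give none.
- Plain comparison: half-width = t(0.95,16) × √ln(1+T²) × √(2/9), with t = 1.746. T = 40% gives 0.73–1.37; T = 60% gives 0.63–1.58.
- Change from own Cycle 1 value: replace ln(1+T²) by 2 ln(1+w²). w = 20% gives 0.79–1.26; w = 30% gives 0.71–1.41.
- The two have equal width when 2 ln(1+w²) = ln(1+T²). For T = 40%, w = √(√1.16 − 1) = 28%. Above that, the change score is worse than ignoring Cycle 1.
- ANCOVA on the Cycle 1 log value: variance ln(1+T²)(1−ρ²), with ρ = 1 − ln(1+w²)/ln(1+T²) and t(0.95,15) = 1.753. This assumes equal variance on both days and ignores chance imbalance in the covariate. For T = 40%, w = 20% gives ρ = 0.74 and 0.81–1.24; w = 30% gives ρ = 0.42 and 0.75–1.34. In both cases it is narrower than the other two methods.

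If only participants 7–18 alternate (6 v 6), the plain comparison at T = 40% has half-width 1.812 × √ln(1.16) × √(2/6), giving 0.67–1.50.

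**The case against.** The objective is exploratory, section 9.4 makes all analyses descriptive, and the committee's decision concerns only whether to add food-effect participants. SAP section 7 says the study stopped before Part B began, so no result is affected. All of this stands and limits the priority.

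Keeping the run-in fasted also has a plausible safety reason. Day 1 Cycle 2 falls after the DLT period, but the run-in review covers cumulative toxicity, and sections 4.1 and 7.1 count DLT-criteria events in Part B whenever they occur. A fed dose of unknown effect would enter that record. This stands as a cost of alternating within the run-in.

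Four stronger readings are tempting, but the documents do not support them:
- *That fed and fasted groups on different doses will be pooled.* The exception clause in 5.3.1 suspends the 9+9 rule after a dose change; the gap is the missing replacement. Nor is a 25% dose step equal to the effect being sought, since no target effect is stated, and under dose proportionality dose-normalising would remove the step.
- *That a matched own-participant reference exists and is ignored.* Cycle 1 has no 8 h sample, and it uses a food restriction of 1 h before and 2 h after the dose, not the 10-hour fast. The analysis was never written, so Cycle 1 data are not excluded either. The unmatched restriction is common to both groups, so it does not bias an adjusted comparison.
- *That the committee's look is fixed at 9 v 6.* The interim analysis is triggered by 15 response-evaluable participants, uses those available for food effect, and falls in a phase when enrolment is normally not paused.
- *That run-in participants are known to differ.* They meet the same criteria. The design simply gives no protection if they do.

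**Conclusion.** The allocation in 5.3.1 aliases food completely with enrolment block in the first 18 participants and puts the whole safety run-in in the fasted group (6 of 6). This follows from the text and needs no assumption. The resulting bias cannot be known; a false ratio of 1.09 to 1.31, or of 0.94 to 0.84 in the other direction, follows from the drifts and run-in shifts assumed above. The rule also leaves allocation undefined after a dose change.

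Using Cycle 1 exposure as a covariate is worthwhile, but its gain depends on CVs the documents do not give. A forced change score could lose precision. Priority is low to moderate; the correction matters if Part B is revived or its text is reused.

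**What to change.** **Allocation (5.3.1).** Alternate Schedules A and B within each dose level from the first Part B participant, and restart the alternation after any dose change. State which participants count towards the 18 in Table 6 once the dose has changed. If the sponsor prefers to keep the run-in on one schedule, alternate from participant 7 and base the food contrast only on the concurrently alternated participants.

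**Analysis (analysis plan).** Keep AUC0-8h and Cmax on Day 1 Cycle 2 as endpoints. Compare fed v fasted on the log scale by ANCOVA, adjusting for the same participant's Cycle 1 log Cmax or log AUC0-6. Take the covariate from Day 8 in 28-day regimens, where the interval since the previous dose matches that of Day 1 Cycle 2, and from Day 1 in 21-day regimens, where Day 1 Cycle 2 follows the drug holiday. Flag participants whose Cycle 2 was delayed under section 6.9.1, since the match then fails. Show the expected precision over a range of CVs.

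**Consistency.** Reconcile the Day 8 sampling times in Table 8 with those in Table 6.

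**Cost.** These are wording changes. The medical monitor already issues the assignment, and no participant or sample is added to the Table 6 schedule. If the run-in alternates, some run-in participants take one fed dose in Cycle 2, while later toxicity is still counted. If it does not, the contrast among the first 18 falls to 6 v 6, with the wider interval shown above.
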